### 9.6.2.3 Descriptive Analysis

#### 9.6.2.3.1 Description of Study Enrollment

A summary of the selection of the study population using flow charts with pre-defined inclusion and exclusion criteria will be presented.

#### 9.6.2.3.2 Description of Subject/Patient Characteristics

Demographic and baseline characteristics, and other covariates will be summarized by cohort of exposure. Discrete variables will be summarized using frequencies and proportions, and continuous variables will be summarized using means and standard deviation (SD) or medians and interquartile range (IQR), as appropriate. Prevalent comorbidities will be described at baseline, as well as any incident conditions that occur during the pregnancy (eg, gestational diabetes). Medications used in the year prior to the LMP date, as well as those used during the pregnancy, will be described.

#### 9.6.2.4 Analysis of the Primary, Secondary, and Exploratory Endpoint(s)

##### 9.6.2.4.1 Analysis of the Primary Endpoint

Frequencies and the proportions (95% CIs) of major congenital malformations, in infants born to the following three cohorts of women with migraine, will be estimated: (1) those exposed to erenumab-aooe immediately prior to or during pregnancy, (2) those exposed to other preventive migraine medications immediately prior to or during pregnancy, and (3) those unexposed to any migraine preventive medications, including erenumab-aooe.

If there is sufficient sample size and adequate overlap in the distribution of confounding variables, formal comparisons to estimate odds ratios and corresponding 95% CIs will be undertaken. We will use inverse probability of treatment weights to address confounding. We will fit a logistic regression model for the conditional probability of treatment,  $Pr(A_i = a|L_i)$ , where  $L_i$  is a vector of measured baseline confounders of the exposure and the outcome. The conditional probability of treatment given a set of covariates is commonly referred to as the propensity score (PS), and a histogram of the overlap in the propensity score will be presented. IP of treatment weights will be constructed as:

$$\widehat{W}_i^2 = \frac{1}{\widehat{Pr}(A_i = a|L_i)}$$

For the analyses described here,  $L_i$  will be based on subject-matter knowledge (see covariates identified in [Section 9.3.3](#)).

##### 9.6.2.4.2 Analysis of the Secondary Endpoints

The proportion of pregnancies ending in spontaneous abortion or stillbirth, and the proportion of live-born infants who are small-for-gestational age in women exposed to erenumab-aooe during pregnancy and in women not exposed to erenumab-aooe before or during pregnancy will be described using frequencies, proportions and corresponding

95th confidence intervals (CI). If there is sufficient sample size and adequate overlap in the distribution of covariates to adjust for key confounders, comparisons will be made using IP-weighted analyses as described in [Section 9.6.2.4.1](#).

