Assuming sufficient power to detect a risk of ratio  $\geq 2.0$  and adequate overlap in the distribution of confounding variables, comparative analyses will be initiated. Balance in covariate distributions will be evaluated by standardized mean differences (SMDs), with an SMD  $< 0.10$  indicating good balance. The potential comparative analyses are summarized below:

- (1) Effect of erenumab-aooe versus other preventive migraine medications on spontaneous abortions (and, separately, stillbirths), in pregnant women with migraine.
- (2) Effect of erenumab-aooe versus other preventive migraine medications on congenital malformations (and, separately, 'small-for-gestational-age'), in live-born infants of women with migraine.

These analyses will be replicated using alternate comparator groups that were unexposed to erenumab-aooe. For the comparative analyses, the effect measure of interest will be the odds ratio (95% CI). We will account for confounding with inverse probability of treatment weights (IPTWs).

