### **8.2 Secondary**

1) To estimate and compare the proportion of pregnancies ending in spontaneous abortions, and, separately, stillbirths among (1) women with migraine directly exposed to erenumab-aooe prior to and during pregnancy, (2) women with migraine exposed to other preventive migraine medications prior to or during pregnancy (comparator group A), and (3) women with migraine not exposed to erenumab-aooe or other preventive migraine medications prior to or during pregnancy (comparator group B).

Comparative analyses will be undertaken if there is sufficient sample size and adequate distribution of covariates to adjust for confounding.

2) To estimate and compare the proportion of live-born infants who are small-for-gestational age among (1) women with migraine directly exposed to erenumab-aooe prior to and during pregnancy, (2) women with migraine exposed to other preventive migraine medications prior to or during pregnancy (comparator group A), and (3) women with migraine not exposed to erenumab-aooe or other preventive migraine medications prior to or during pregnancy (comparator group B). Comparative analyses will be undertaken if there is sufficient sample size and adequate distribution of covariates to adjust for confounding.

3) To describe demographic and clinical characteristics, risk factors for adverse pregnancy outcomes, fetal outcomes, and infant outcomes, and medication treatment patterns during pregnancy in both exposed and unexposed cohorts of women with migraine.

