### **9.6.2.5 Sensitivity Analysis**

#### **9.6.2.5.1 Subgroup Analysis**

Subgroups that will be explored if there is sufficient sample size include maternal age group at LMP (16-17 years, 18-40 years, 41-44 years), calendar year at LMP, comorbidities or medication use at baseline, concomitant medication use during pregnancy, dose of erenumab-aooe taken (70 or 140 mg), and patients who have migraine with aura or chronic migraine.

In addition to assessing outcomes in pregnant women exposed to erenumab-aooe before or during pregnancy and those not exposed to erenumab-aooe before or during pregnancy, we will also explore proportions of each of the outcomes in subgroups of the unexposed cohort, including migraine patients exposed to other CGRPs, migraine patients exposed to erenumab more than 112 days prior to the estimated date of conception and not during the pregnancy, migraine patients exposed to other preventive migraine medications, and migraine patients exposed to known teratogens in the one month prior to or during pregnancy. Also, outcomes will be described in migraine patients with claims for acute medication during the pregnancy.

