### **9.6.3 Analysis of Safety Endpoint(s)/Outcome(s)**

This is a study to assess the safety of erenumab-aooe on maternal and fetal outcomes when mothers are exposed to erenumab-aooe during pregnancy. Safety outcomes include major congenital malformations in infants, pregnancies ending in spontaneous abortion or stillbirth, and infants who are small-for-gestational age. The proportion of live-born infants who have major congenital malformations or are small-for gestational age, and the proportion of pregnancies ending in spontaneous abortion or stillbirth will be estimated in an erenumab-aooe-exposed cohort and in an unexposed cohort of pregnant women with migraine.

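### For the secondary outcomes, Sections 9.6.2.4.2 and 9.6.3 use one group unexposed to erenumab where the objectives require comparators A and B separately, so the protocol contradicts itself on the reference group

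*Protocol*

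**What the plan says.** - **Section 8.2** sets the erenumab cohort beside "women with migraine exposed to other preventive migraine medications prior to or during pregnancy (comparator group A), and (3) women with migraine not exposed" to any preventive (comparator group B). It does this for spontaneous abortion and stillbirth, and again for small-for-gestational-age. The objectives in the abstract match.
- **Abstract, Comparative Analyses**, lists as a planned contrast "Effect of erenumab-aooe versus other preventive migraine medications on spontaneous abortions (and, separately, stillbirths), in pregnant women with migraine". A second item does the same for small-for-gestational-age. Both are to be repeated with other groups not exposed to erenumab.
- **Section 9.6.2.4.1** (primary endpoint) estimates malformations in three cohorts and keeps A and B apart.
- **Section 9.6.2.4.2** (secondary endpoints) describes outcomes in women exposed to erenumab during pregnancy and in "women not exposed to erenumab-aooe before or during pregnancy will be described using frequencies". A and B are not mentioned. If sample size and overlap suffice, "comparisons will be made using IP-weighted analyses as described in" Section 9.6.2.4.1; the comparator is not named.
- **Section 9.6.3** says that the proportions for all four outcomes "will be estimated in an erenumab-aooe-exposed cohort and in an unexposed cohort of pregnant women with migraine".
- **Section 9.6.2.5.1** restates the exposed versus not-exposed split and adds that "we will also explore proportions of each of the outcomes in subgroups of the unexposed cohort". Users of other preventive migraine medications are one of the subgroups listed.

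**The concern.** The objectives and the section that should carry them out name different reference groups. An analyst who follows Section 9.6.2.4.2 would report two proportions per secondary outcome where Section 8.2 needs three, and would have to guess the comparator for the odds ratio. An analyst who follows Section 9.6.3 would do the same for malformations, against Section 9.6.2.4.1.

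The choice matters because A and B answer different questions. Women who take erenumab plausibly have migraine severe enough to need prevention. Claims capture severity only through proxies, such as codes for aura or chronic migraine (Section 9.3.3), and Section 9.8.1.3 concedes residual confounding. Comparing with users of other preventives is the design's main protection against confounding by severity. A reference group made up mostly of untreated women gives that protection up and largely answers the B question.

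**Working it through.** **Step 1. Sections side by side (reference group for the secondary outcomes).**
- Section 8.2 and the abstract's objectives: A and B, separately.
- Abstract, Comparative Analyses: A first, then other groups unexposed to erenumab.
- Section 9.6.2.4.2, description: one group not exposed to erenumab.
- Section 9.6.2.4.2, comparison: not named; method taken from Section 9.6.2.4.1, which has three cohorts.
- Section 9.6.3: one unexposed cohort, for malformations as well.
- Section 9.6.2.5.1: A's members are a subgroup of the unexposed cohort.

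The unexposed cohort of Section 9.6.2.5.1 also lists users of other CGRP drugs and of known teratogens. Section 9.2.2.2 excludes both when exposure falls within five half-lives before LMP. So the single cohort is not clearly A plus B either.

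**Step 2. What a single unexposed group would contain.** The protocol states no composition, so there is no figure of its own to reproduce. Inputs from the abstract and Sections 9.2.3 and 9.5: 0.9% of pregnant women with migraine treated with a preventive during pregnancy; about 7,000 such women a year in MarketScan; 1,400-1,500 exposed to erenumab over 9 to 10 years; 1:4 matching.

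- *Unmatched pool, 0.9% taken as the other-preventive share.* 1 - 0.009 = 99.1% without a preventive. With erenumab women removed: 1 - (0.009 × 63,000)/(63,000 - 1,400) = 1 - 567/61,600 = 99.08%; over 10 years, 1 - 630/(70,000 - 1,500) = 99.08%.
- *Random 1:4 sample from that pool.* 4 × 1,400 = 5,600 to 4 × 1,500 = 6,000 women, of whom 0.009 × 5,600 = 50 to 0.009 × 6,000 = 54 use another preventive.
- *Other-preventive share of 2%, 5% or 10% (assumed range).* Section 9.2.2.1 also counts use within five half-lives before LMP for A, so A's share should exceed a during-pregnancy figure. The pool is then 98%, 95% or 90% without a preventive.
- *A limited to its 0.9% supply (567-630 women), B matched 1:4.* 5,600/(5,600 + 630) = 89.9% to 6,000/(6,000 + 567) = 91.4%.
- *A and B each matched 1:4, then pooled.* 50%. On the 0.9% figure, MarketScan would supply 567-630 women for A against the 5,600-6,000 needed.

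**Step 3. How far the 0.9% can be trusted.** 0.009 × 7,000 × 9 to 10 years = 567-630 women on any preventive. The same paragraph projects 1,400-1,500 on erenumab alone, which is 1,400/70,000 = 2.0% to 1,500/63,000 = 2.4%. The two figures do not fit together, so the 99% result is conditional.

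**Step 4. Why the mix matters (illustration with assumed crude risks).** Take 6% in the erenumab cohort, 6% in A and 3% in B, so erenumab does no worse than A. The pooled reference risk is f × 6% + (1 - f) × 3%, where f is A's share.
- f = 0.9%: reference 3.03%, risk ratio 6/3.027 = 1.98.
- f = 50%: reference 4.5%, risk ratio 6/4.5 = 1.33.
- Against A alone 1.00; against B alone 2.00.

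The unadjusted result is set by the mix. Weighting removes the difference only so far as severity is measured.

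**The case against.** The strongest reply is that the plan never states a pooled comparison. In Section 9.6.2.4.2 the two-group wording governs only the description. The comparison sentence borrows from Section 9.6.2.4.1, which has three cohorts. Section 9.6.3 speaks of estimating proportions and specifies no contrast. The abstract keeps erenumab versus other preventives for these same outcomes, and Sections 9.2.2 and 9.3.1 define A and B for the whole study. Section 9.6.2.5.1 presents its subgroups as additional work.

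All of this stands, and it limits the point. A reader might infer that the protocol pools A and B throughout and that the active-comparator contrast is lost. The documents do not support that, because the abstract and Section 8.2 both retain it. A reader might also infer that the reference group would be about 99% untreated, with some 50-54 preventive users. That rests on a during-pregnancy figure that is not A's share, on one pooled 1:4 sample that the plan does not describe, and on a percentage that conflicts with the plan's own projection.

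The reply does not remove the contradiction. Section 9.6.2.4.2 is the body section for these endpoints, its description is incompatible with Section 8.2, and it leaves the comparator for the formal analysis undetermined. This is not detail deferred to an SAP, since the protocol itself states incompatible groups.

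**Conclusion.** The protocol is inconsistent on the reference group for spontaneous abortion, stillbirth and small-for-gestational-age and, through Section 9.6.3, for malformations. The contradiction follows from the text and depends on no number.

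The size of the consequence is conditional on Sections 9.6.2.4.2 and 9.6.3 being followed as written. The reference would then mix treated and untreated women and would probably be mostly women without a preventive. The share ranges from about 99% down to 50%, depending on how the group is formed and on how common other-preventive use is over the full exposure window. At either end it would not answer the erenumab versus A question. The premise that preventive users have more severe migraine is a plausible judgement and not a figure from the protocol. The text should be corrected; the three-cohort design itself is sound.

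**What to change.** - In Sections 9.6.2.4.2 and 9.6.3, replace the single unexposed cohort with the three cohorts of Sections 8.2 and 9.6.2.4.1.
- For each outcome, report the proportion (95% CI) in erenumab, A and B. State two IP-weighted contrasts, erenumab versus A and erenumab versus B, without pooling A and B.
- Align Section 9.6.2.5.1 so that users of other preventives are comparator A and not an exploratory subgroup.

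This reuses the sponsor's own design. It costs protocol wording and some extra analysis; the form of the propensity models can be left to the SAP. The contrast with A will be less precise than a pooled one. For example, suppose A held only 567 women against 1,400 on erenumab, with similar risks and before weighting. The standard error of a risk difference would be √[(1/1,400 + 1/567)/(1/1,400 + 1/5,600)] = √(0.002478/0.000893) ≈ 1.7 times that of a pooled 1:4 contrast. That loss is the price of answering the stated question.

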### **9.6.2.5 Sensitivity Analysis**

#### **9.6.2.5.1 Subgroup Analysis**

Subgroups that will be explored if there is sufficient sample size include maternal age group at LMP (16-17 years, 18-40 years, 41-44 years), calendar year at LMP, comorbidities or medication use at baseline, concomitant medication use during pregnancy, dose of erenumab-aooe taken (70 or 140 mg), and patients who have migraine with aura or chronic migraine.

In addition to assessing outcomes in pregnant women exposed to erenumab-aooe before or during pregnancy and those not exposed to erenumab-aooe before or during pregnancy, we will also explore proportions of each of the outcomes in subgroups of the unexposed cohort, including migraine patients exposed to other CGRPs, migraine patients exposed to erenumab more than 112 days prior to the estimated date of conception and not during the pregnancy, migraine patients exposed to other preventive migraine medications, and migraine patients exposed to known teratogens in the one month prior to or during pregnancy. Also, outcomes will be described in migraine patients with claims for acute medication during the pregnancy.

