#### **9.2.2.2 Exclusion Criteria**

Women who are exposed to known teratogens (eg, valproate or topiramate) or other CGRP antagonists will be excluded if exposure to these substances occurs within five of their half-lives prior to LMP.

For comparator cohort B, women who have pharmacy claims for any preventive migraine medications will be excluded.

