### **9.3 Variables**

#### **9.3.1 Exposure Assessment**

Pregnant women who have pharmacy claims for erenumab-aooe (identified using NDC codes) in the 112 days prior to the LMP date (to allow for the half-life of erenumab) or during the pregnancy will be considered exposed to erenumab-aooe.

Exposure to erenumab-aooe will be categorized by dose (70 mg versus 140 mg), by length of exposure, and by timing in relation to trimester of pregnancy: before the last menstrual period (LMP, in the 112 days prior to the EDC, this is the exposure window of interest for major malformations), during the first trimester (from the LMP to 90 days after the LMP), during the second trimester (from day 91 after the LMP to day 180 after the LMP), and during the third trimester (from day 181 after the LMP to the end of pregnancy) (see [Section 9.3.1.1](#) for definitions of LMP).

For the comparator cohorts, comparator group A will include pregnant women with migraine who do not have pharmacy claims for erenumab-aooe in the 112 days prior to the LMP but do have evidence of the use of other preventive migraine medications. Comparator group B will include pregnant women with migraine who do not have pharmacy claims for erenumab-aooe or other anti-CGRP medications 112 days prior to the LMP date or during pregnancy

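### The exclusion in 9.2.2.2 removes, from the other-CGRP and known-teratogen subgroups planned in 9.6.2.5.1, the women exposed closest to the LMP

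*Protocol*

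**What the plan says.** Section 9.2.2.2 (Exclusion Criteria) opens with a rule that is tied to no single cohort: "Women who are exposed to known teratogens (eg, valproate or topiramate) or other CGRP antagonists will be excluded". The condition attached is timing: such women "will be excluded if exposure to these substances occurs within five of their half-lives prior to LMP". Exposure during pregnancy is not mentioned. The next sentence of that section is limited to one cohort: "For comparator cohort B, women who have pharmacy claims for any preventive migraine medications will be excluded".

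Section 9.6.2.5.1 (Subgroup Analysis) then says that proportions of each outcome will be explored "in subgroups of the unexposed cohort, including migraine patients exposed to other CGRPs", with no exposure window for that group. The same list includes "migraine patients exposed to known teratogens in the one month prior to or during pregnancy".

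The Study Design Schema defines the comparator cohort only by the absence of erenumab claims in the 112 days before the LMP or during pregnancy. Section 9.3.1 defines comparator B more tightly, as women "who do not have pharmacy claims for erenumab-aooe or other anti-CGRP medications 112 days prior to the LMP date or during pregnancy".

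**The concern.** One rule removes women whom another rule sets out to report. If a programmer applies eligibility first and then forms the subgroups, the two tables will lack the women whose exposure came nearest the LMP. For erenumab itself, section 9.3.1 names the period before the LMP as the window of interest for major malformations, so this is not an incidental part of the exposure history. A table labelled as teratogen-exposed or other-CGRP-exposed would not tell its reader that these women are missing.

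If a programmer instead keeps these women in the unexposed cohort so that the subgroups are complete, section 9.2.2.2 is breached and the comparators hold women whom the protocol meant to leave out. The analyses are run separately in two databases, so each could be programmed in good faith on a different reading.

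**Working it through.** The protocol states no figure on this point, so there is nothing to reproduce. The check is a comparison of the two rules, with one piece of arithmetic on the windows.

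**Step 1: scope of the exclusion.** The first sentence of 9.2.2.2 names no cohort, while the second is limited to comparator B. The authors narrowed the scope where they meant to, so the first sentence reads as applying to the whole study.

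**Step 2: parent population of the subgroups.** Section 9.6.2.5.1 calls them subgroups of the unexposed cohort. That cohort must be broader than comparator B, because the same list includes users of other preventive migraine medications, whom 9.2.2.2 bars from B. The broad definition in the Study Design Schema fits. The general exclusion still applies to that broader cohort.

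**Step 3: who is left when both rules apply.**

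| Timing of exposure to a teratogen or other CGRP drug | 9.2.2.2 | Available to the subgroup? |
|---|---|---|
| Within five half-lives before LMP, then stopped | Excluded | No |
| Within five half-lives before LMP, continuing into pregnancy | Excluded | No |
| Before LMP only, earlier than five half-lives | Kept | Other-CGRP: yes, as no window is set. Teratogen: only if within the month before pregnancy |
| First exposed after LMP | Kept | Yes |

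The subgroups are therefore depleted at the LMP end and are not empty.

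**Step 4: how much of the pre-LMP month is removed.** Let h be the half-life in days. Take the month as 30 days, pregnancy as starting at the LMP, and exposure as dated to a single day. The excluded share of the month is min(1, 5h/30). The protocol gives no half-lives, so the values of h are assumptions.

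| h (days, assumed) | Excluded days, 5h | Share of the month |
|---|---|---|
| 0.5 | 2.5 | 2.5/30 = 8% |
| 1 | 5 | 5/30 = 17% |
| 3 | 15 | 15/30 = 50% |
| 6 or more | 30 or more | 100% |

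The part removed is always the part next to the LMP. These are shares of calendar time, not of women; the protocol gives no distribution of fills from which to convert one to the other.

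**Step 5: long half-life drugs.** If erenumab's 112-day window is read as five half-lives, it implies 112/5 = 22.4 days. Another CGRP antibody with that half-life (an assumption) would carry a 112-day exclusion. Its subgroup would then hold only women last exposed more than 112 days before the LMP or first exposed after it.

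**Step 6: dating of exposure.** Section 9.2.2.2 does not say whether a fill date or the days' supply decides. On fill dates, a short half-life drug loses only women who filled in the last few days before the LMP. On days' supply, every woman whose supply runs up to or past the LMP is excluded, whatever the half-life. The same text therefore allows small or large depletion.

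**The case against.** The strongest reply is that this is an order-of-operations matter which a SAP would normally settle, and that the protocol plainly tolerates relaxed eligibility in exploratory work. Section 9.6.2.5.3 admits women with only 180 days of enrolment, erenumab users with no migraine diagnosis, and infants without 90 days of follow-up. Drawing two descriptive groups before an exclusion would fit that pattern. This stands in part: it shows that the fix is in keeping with the protocol. But those analyses say that they depart from the eligibility rules, whereas 9.6.2.5.1 does not and places its groups inside the unexposed cohort. The protocol fixes both rules, so the conflict is in its text and is not detail left for later.

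It is also fair to say that different windows for an exclusion and for a descriptive subgroup are not wrong in themselves. They need explaining here only because one cuts into the other.

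Several stronger readings are tempting, and the documents do not support them:

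- **That the subgroups are empty, or that everyone with drug on board at conception is gone.** The exclusion is anchored to the LMP, which precedes conception, and is silent on exposure during pregnancy. A woman who first fills after the LMP stays in, even if that is before conception, and she may be heavily exposed.
- **That a positive control is lost and the malformation results would falsely reassure.** The protocol gives the teratogen subgroup no such role and attaches no test or decision to it. Putting a size on the bias would require giving the retained women background risk, which assumes the answer.
- **That the other-CGRP subgroup contradicts comparator B.** Having no such users is how B is meant to work, and step 2 shows that the subgroups are not drawn from B.

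**Conclusion.** The contradiction is real and narrow. Section 9.2.2.2 excludes, without exception, women whom 9.6.2.5.1 intends to describe, and no passage says which rule is applied first. Following both leaves out the women exposed nearest the LMP, including continuing users whose pre-LMP exposure falls in the excluded window.

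The size is not determined by the document. It rests on half-lives and an exposure-dating rule that are not given; the 8% to 100% range illustrates the overlap of windows and does not estimate how many women are lost. The overlap is potentially largest for long half-life CGRP antibodies.

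The consequence is confined to exploratory, descriptive subgroup results that are themselves conditional on sample size. A reader might infer that the primary comparison is compromised. It is not, provided that the exclusion is applied as written to the main cohorts. This is a minor point, worth correcting because it is cheap and changes what two tables mean.

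**What to change.** In 9.6.2.5.1, state that the other-CGRP and known-teratogen groups are drawn from otherwise eligible women with migraine before the 9.2.2.2 exclusion is applied, and are reported as separate descriptive groups. Add that women re-admitted in this way do not enter the erenumab, A or B cohorts used for the main comparisons.

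Keep that last sentence to re-admitted women. A blanket rule that no teratogen or other-CGRP user may enter a comparator denominator would also remove women first exposed during pregnancy, whom 9.2.2.2 does not exclude. Since section 7.1 lists topiramate and divalproex among the common preventives, such a rule could alter comparator A and hence the primary comparison.

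Reconcile the pre-LMP windows in the two sections, give the other-CGRP subgroup a window, and state in 9.2.2.2 whether exposure is dated by fill or by days' supply and whether the exclusion also covers exposure during pregnancy.

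The cost is wording in the protocol and SAP, and a small amount of descriptive tabulation from the same two databases. One caution: if the clarification extends the 9.2.2.2 exclusion into pregnancy, the main cohorts change, so that choice should be made deliberately and its effect on comparator A checked.
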